6.1.1 DOSING SCHEDULES

- 1) Patients with Stage II (non-contiguous), Stage III and Stage IV Follicular lymphoma and Marginal zone lymphoma will receive ublituximab 900 mg IV weekly for 4 doses (days 1, 8, 15 and 22)
- 2) At 8 weeks after completion of ublituximab monotherapy, patients will undergo PET-CT assessment.
- 3) Patients who do not achieve a CR after ublituximab monotherapy will receive a combination of ublituximab and umbralisib for a total of 12 cycles given as follows: ublituximab 900 mg IV on Days 1, 8 and 15 during the first cycle of combination treatment, on Day 1 of each subsequent 28-day cycle through Cycle 6 and then every 3 cycles (i.e. C9 and C12) PLUS umbralisib 800 mg PO daily on Days 1-28 of each 28-day cycle.

4) Patients with CR on either single or combination therapy will be followed with scans for 2 years.

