7.3.7 FOLLOW-UP

The follow-up period begins upon all study treatment discontinuation or completion as per protocol. This includes subjects who complete the full course of treatment and who discontinue treatment due to progression or toxicity, as well as those who discontinue before progression to pursue a new anti-lymphoma therapy.

All subjects will be followed by provider for AEs and concomitant medications/procedures for 30 days after the last dose of ublituximab (for single agent treatment) and for 30 days after the latest of last dose of ublituximab or the last dose of umbralisib (for combination therapy).

The following evaluations will be performed at the follow-up visits:

- History and physical exam including vital signs and weight
- Laboratory evaluation (Hematology and Chemistry)
- AEs and concomitant medications will be evaluated

Patients will be seen in follow up every 3 months for the first 2 years post completion of therapy (last dose of ublituximab (for single agent treatment) and umbralisib (for combination therapy). PET/CT scans will be performed at the 6 months, 12 months, 18 months and 24 months post completion of therapy (last dose of ublituximab for single agent treatment) and umbralisib (for combination therapy). (If Baseline PET/CT for marginal zone lymphoma patients does not

demonstrate uniformly FDG avid lesions subsequent assessments on the study will be done with CT scans of the neck, chest, abdomen and pelvic scan with contrast ONLY) At this time, patients will be seen by a provider for follow up of PD, subsequent anti-lymphoma therapy, or death. If at any point a patient decides to withdraw from long-term follow-up, there must be documentation of this decision by the provider, nurse or coordinator.

Subject self-reported health related quality of life using FACT-Lym questionnaire will be assessed at the 6 months, 12 months, 18 months and 24 months post completion of therapy (last dose of ublituximab (for single agent treatment) and the latest of last dose of ublituximab or the last dose of umbralisib (for combination therapy).

Research blood tubes may be collected at the 6 months, 12 months, 18 months and 24 months post completion of therapy (last dose of ublituximab (for single agent treatment) and the latest of last dose of ublituximab or the last dose of umbralisib (for combination therapy) for correlative analysis as described in this protocol

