- Screening bone marrow biopsy must be performed ≤ 6 months prior to study registration.
- 12-lead single electrocardiogram (ECG) will be recorded.
- Research blood samples (may be collected at screening and at all time-points when a PET CT is performed (i.e EOInduction, Prior to C4,8,12 of combination therapy, EOT, 6,12,18 and 24 months and at recurrence/progression) for correlative analysis as described in this protocol. Research samples will be collected and stored under the LTB protocol. Patients must be tissue bank consented prior to sample collection and samples will be collected by the tissue banking team.
- If screening assessment are performed within 48 hours of C1D1, safety laboratory and physical examinations need not be repeated at Cycle 1.
- Measurements can be done off the CT images of a PET/CT. (If Baseline PET/CT for marginal zone lymphoma patients does not demonstrate uniformly FDG avid lesions subsequent assessments on the study will be done with CT scans of the neck, chest, abdomen and pelvic scan with contrast ONLY

Protocol # 18-2128

PI: [name]

Version Date: May 17, 2021

11. Repeat bone marrow only required for MZL patients to confirm CR if initial bone marrow was positive. This will be arranged +/- 7 days of this visit. On the combination arm, a bone marrow biopsy (if initially involved for MZL) will be done 3 months post completion of 12 cycles of therapy.
12. During the induction treatment, patients will dose according to Dosing Schedule.
13. Hematology blood draws can be done before administration (not more than 2 days apart)
14. EOI PET CT will be performed within 8 weeks (+/- 7 days) post completion of single agent induction therapy. If PET positive after the completion of single agent induction therapy, a biopsy of PET positive area may be done at MD discretion. (If Baseline PET/CT for marginal zone lymphoma patients does not demonstrate uniformly FDG avid lesions subsequent assessments on the study will be done with CT scans of the neck, chest, abdomen and pelvic scan with contrast ONLY)
15. The first cycle of Combination therapy will start (+ 2 week) after End of Induction imaging scan for patients not in CR. Patients on combination therapy will be seen at D1, D8 and D15 for C1, and D1 and D15 for C2 and then seen every 4 weeks for the remaining duration of therapy .

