22. Hepatitis B virus (HBV) testing will include hepatitis B surface antigen (HBsAg), antibody to the hepatitis B surface antigen (anti-HBs), and antibody to the hepatitis B core antigen (anti-HBc). If a subject is anti-HBc or HBsAg positive, a quantitative polymerase chain reaction test to measure viral DNA load.
23. Testing for HCV (testing for antibody; if positive then quantitative polymerase chain reaction test to measure viral RNA load), CMV testing by PCR every 3 cycles during treatment. HIV testing will be performed per institutional guidelines.
24. A microscopic examination will be performed if urinalysis result is abnormal.
25. Research samples to be collection prior to C4,C8 and C12 on combination therapy for correlative analysis as described in this protocol
26. 6 months, 12 months, 18 months and 24 months post completion of therapy – last dose of ublituximab (for single agent treatment) and umbralisib (for combination therapy)
27. Subject self-reported health related quality of life (FACT-LYM) will be assessed at screening and at all time-points when a PET CT is performed (i.e EOInduction, Prior to C4,8,12 of combination therapy, EOT, 6,12,18 and 24 months)
28. 4 weeks after last dose of Single agent Induction and Combination therapy patients will be seen in clinic for history and physical exam including vital signs and weight, lab evaluation including CBC and chemistry and AEs and concomitant medications.
29. All laboratory, safety, and physical examinations should be performed by a provider or nurse within 48 hours of the start of every dose.
30. Ublituximab will be administered every cycle (28 days) through Cycle 6, and then every 3 cycles (i.e. at Cycle 9 and Cycle 12).

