10.4.10 EXPLORATORY ANALYSES

Secondary endpoints may lead to exploratory analyses outlined in 10.4.3.

Overall response rate, CR rate, PR rate, PD rate, and SD rate will be summarized for both the FL and MZL cohorts upon study completion.

Progression free survival (PFS) is defined as time from enrollment to PD or death of any cause. Patients who pass away without PD will be counted as if PD occurred on date of death. Patients without PD and did not pass away but are lost to follow up will have their information censored at date of most recent tumor assessment.

Overall survival is defined as time from enrollment to death due to any cause.

Median measures for 2-yr PFS and OS as well as remission duration will be assessed by conducting survival analysis. Kaplan-Meier survival methods will be used to estimate the survival function of these time-to-event outcomes.

Baseline disease and patient factors will be summarized.

Rates of transformation to aggressive lymphoma will be calculated.

Any assessment of minimum residual disease or assessment of next-generation sequencing will be analyzed.

QOL analysis will be performed: The change in Quality of life (QoL) scores as measured by FACT-Lym at the start of therapy and at the end of study will be assessed using a paired t-test and a null hypothesis of no change in QoL over the course of the study. Assessment of EuroQOL questionnaire has been shown in the **Appendix** section.

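### The FACT-Lym paired t-test uses two of 6 or 10 scheduled forms and pools both treatment paths at an end of study that is never defined

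*Combined protocol and SAP*

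**What the plan says.** Section 10.4.10 names a single quality-of-life analysis. FACT-Lym scores "at the start of therapy and at the end of study will be assessed using a paired t-test", against a null of no change. It names no visit in between, gives no rule for missing forms and does not split by treatment path.

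Collection is much richer. Footnote 27 to the Schedule of Events (section 7.4) reads: "Subject self-reported health related quality of life (FACT-LYM) will be assessed at screening and at all time-points when a PET CT is performed". It lists the later visits as "EOInduction, Prior to C4,8,12 of combination therapy, EOT, 6,12,18 and 24 months". Sections 7.3.3, 7.3.4, 7.3.5 and 7.3.7 confirm these visits one by one. For follow-up, section 7.3.7 says that FACT-Lym "will be assessed at the 6 months, 12 months, 18 months and 24 months post completion of therapy".

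Quality of life is an exploratory objective (section 3). Section 2.2 counts better understanding of it among the study's benefits to society.

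**The concern.** There are three weaknesses.

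- **Unused forms.** A first-versus-last comparison ignores the forms before C4, C8 and C12. These are the only ones scheduled while patients take umbralisib, which is when toxicity would be expected to show in quality of life.
- **Undefined end point.** The study has two paths of very different length. One pooled change to an undefined end of study may average a score taken soon after a short course with one taken long after a year of treatment.
- **Early leavers.** Without a rule, the analyst decides after seeing the data whether an exit form counts.

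At stake is whether the result can be interpreted. The mean change would belong to no stated time since treatment and would say nothing about the treatment period itself.

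**Working it through.** **1. The plan's own figures.** No alpha, standard deviation, target change or sample size is given for quality of life, so there is no such figure to reproduce. The only power statement concerns the primary CR test: 24 patients, 30% versus 50%, one-sided 0.10, 73% power. The exact binomial test that rejects at 11 or more CRs has alpha 0.074 and power 0.729, which matches. Nothing below touches it.

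**2. Forms per patient (section 7.4, footnote 27).**
- Induction only: screening, end of induction (EOI), 6, 12, 18 and 24 months = 6. Unused: (6 − 2)/6 = 67%.
- Combination: the same 6 plus pre-C4, pre-C8, pre-C12 and end of treatment (EOT) = 10. Unused: (10 − 2)/10 = 80%.

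The split between paths is not known in advance. As an assumed range, let 30% to 50% of 24 patients stop after induction, with every form completed:
- 30%: 7 × 6 + 17 × 10 = 212 forms. The test uses 24 × 2 = 48 and leaves out 164 (77%).
- 50%: 12 × 6 + 12 × 10 = 192 forms. The test leaves out 144 (75%).

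**3. When the end form falls.** Days are counted with first dose as day 1, a month as 30.44 days and 24 months as 730 days.
- The last induction dose is on day 22. Section 6.1.1: "At 8 weeks after completion of ublituximab monotherapy, patients will undergo PET-CT assessment". The EOI scan is therefore on day 22 + 56 = 78.
- Section 7.4, footnote 15: "The first cycle of Combination therapy will start (+ 2 week) after End of Induction imaging scan". Combination start is therefore on day 78 to 92.
- Section 6.1.1 plans the "combination of ublituximab and umbralisib for a total of 12 cycles given as follows", and each cycle is 28 days: 12 × 28 = 336 days. The last umbralisib dose is on day 413 to 427.
- The EOT scan is 12 weeks later (section 7.1): day 497 to 511.

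| Reading of end of study | Induction only | Combination | Difference |
|---|---|---|---|
| 24 months after last dose (7.3.7) | day 752 | day 1143–1157 | 391–405 days (12.8–13.3 months) |
| 24 months after EOI or EOT scan (7.1; 7.4, footnote 21) | day 808 | day 1227–1241 | 419–433 days (13.8–14.2 months) |
| EOI or EOT visit (study ends when planned treatment is complete, 4.1 and 8.5) | day 78 | day 497–511 | 419–433 days |
| Last form within 2 years of enrollment (synopsis, 4.1), clock from last dose | day 570 | day 596–610 | 26–40 days |
| The same, clock from scan | day 626 | day 680–694 | 54–68 days |

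The last two rows take first dose as the date of enrollment. Under that cap only 5 and 7 forms fall due, so 3 of 5 (60%) or 5 of 7 (71%) are unused.

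**4. Early leavers.**
- Section 6.1.2 asks for an end of study visit on withdrawal of consent or progression, but section 7 and the schedule list no visit by that name.
- Section 7.3.5 provides an EOT visit, with FACT-Lym, for patients who come off treatment early.
- Section 7.3.8 gives early termination visits the same content as the EOT visit.
- Sections 5.4.2 and 7.3.7 keep patients who only stop drug in follow-up, with later forms due.

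If an exit form counts as end of study, scores from soon after withdrawal are averaged with scores taken much later. If it does not, those patients drop out of the paired test unless they complete later forms. Patients who die, are lost or refuse before giving any later form are dropped either way.

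**5. Scale of what can be detected.** Assuming two-sided 5% and 80% power, the noncentral t distribution gives a detectable mean change, in SDs of the change score, of 0.60 with 24 pairs, 0.72 with 17 and 0.89 with 12.

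**The case against.** A paired t-test is a valid, simple choice for 24 patients in an exploratory section. It carries no allocated alpha and has no bearing on the primary test. Nothing in the plan prevents descriptive summaries of the other visits. This stands, and it limits the weight of the point.

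Three stronger readings are tempting, and the documents do not support them.

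- A reader might infer that patients who progress or withdraw have no end form. Sections 5.4.2, 6.1.2, 7.3.5, 7.3.7 and 7.3.8 give most of them an exit visit or continued follow-up. What is missing is a rule on which form counts.
- A reader might infer that the end forms are always more than a year apart. That follows from the visit schedule and from the EOI/EOT reading, but not if follow-up is capped at 2 years from enrollment.
- A reader might infer that a mixed model cures dropout bias or is shown to gain precision. It relies on dropout being explained by the scores already recorded. If patients stop reporting because of a decline that no form captured, the bias largely remains. No precision gain has been demonstrated, and contrasts confined to combination patients use fewer patients than the pooled test.

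It is also fair to object that contrasts only to EOI and EOT would miss the treatment period. EOI is 8 weeks after the last induction dose, and for completers EOT is 12 weeks after the combination. The on-treatment visits therefore need contrasts of their own.

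**Conclusion.** The point holds as a cheap improvement. On the full visit schedule the planned test leaves out 67% of forms for induction-only patients and 80% for combination patients, including all forms planned before C4, C8 and C12. The end of study is not defined for a patient. The timing difference between paths is about 13 to 14 months on the visit-schedule and EOI/EOT readings, and about 1 to 2 months under a 2-year cap from enrollment. The treatment of exit forms is left open.

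These figures rest on the protocol's visit timing without visit windows or treatment delays. The share of patients on each path is assumed, as are the alpha and power behind the detectable changes. The gain from changing the analysis is use of all forms at stated times within each path. It is not a cure for missing data. The primary CR analysis is unaffected.

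**What to change.** In section 10.4.10, replace the paired t-test with a repeated-measures mixed model on all FACT-Lym forms. Use visit as a factor and patient as a random effect, and model post-induction visits separately by path (induction only, combination). Without that separation, follow-up visits with the same label would pool unlike times since first dose.

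Prespecify these contrasts:
- screening to end of induction, in all patients;
- screening to pre-C4, pre-C8, pre-C12 and EOT, in combination patients.

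If a paired t-test is kept as supportive, define end of study for each path and state whether exit forms count. Report the number of forms received by visit and path, so that readers can judge the missing data.

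The cost is a paragraph of text and modest extra analysis, with no new data collection. The combination contrasts rest on fewer patients. With the assumed 17 or 12 combination patients, a simple paired comparison would detect 0.72 or 0.89 SD, against 0.60 SD with all 24. Bias from informative dropout would remain and should be acknowledged in the report.

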10.5 SAMPLE SIZE

The study will enroll 24-30 patients.

10.6 MEASURES TO MINIMIZE BIAS

In this non-blinded phase II study outcomes will be assessed by the principal investigator.

11 SOURCE DOCUMENTS AND ACCESS TO SOURCE DATA/DOCUMENTS

To ensure the privacy and confidentiality of data for this protocol, the data will be stored on a restricted access server. Access to the project directory containing the data will be limited to the investigators and research staff. Information about data security awareness is promoted through user training and education and supplemented by policies and procedures. Password protection will

be used for all transactions that involve viewing, editing, and analyzing the data or that provide access to data fields derived from the original source documents.

12 QUALITY ASSURANCE AND QUALITY CONTROL

Quality Control (QC) procedures will be implemented beginning with the data entry system and data QC checks that will be run on the database will be generated. Any missing data or data anomalies will be communicated to the site(s) for clarification/ resolution.

Following written SOPs, the study monitor will verify that the clinical trial is conducted and data are generated, documented (recorded), and reported in compliance with the protocol, GCP, and the applicable regulatory requirements (e.g., Good Laboratory Practices (GLP), Good Manufacturing Practices (GMP)).

The investigational site will provide direct access to all trial-related sites, source data/ documents, and reports for the purpose of monitoring and auditing by the DSMC audit team, and inspection by local and regulatory authorities.

13 ETHICS/PROTECTION OF HUMAN SUBJECTS

13.1 ETHICAL STANDARD

The PI will ensure that this study is conducted in full conformity with regulations for the Protection of Human Subjects of Research codified in 45 CFR Part 46, 21 CFR Part 50, 21 CFR Part 56. ICH E6 may also be followed to the extent it has been adopted by and is in accordance with FDA regulations.

13.2 INSTITUTIONAL REVIEW BOARD

The protocol, informed consent form(s), recruitment materials, and all subject materials will be submitted to the Colorado Multiple Institutional Review Board (COMIRB) for review and approval. Approval of both the protocol and the consent form must be obtained before any subject is enrolled. Any amendment to the protocol will require review and approval by TG Therapeutics, Inc. and by COMIRB before the changes are implemented to the study. All changes to the consent form will be COMIRB approved; a determination will be made regarding whether previously consented participants need to be re-consented.

13.3 INFORMED CONSENT PROCESS

The Consent Forms must be signed and dated by the patient or the patient's legally authorized representative before his or her participation in the study. The case history or clinical records for each patient shall document the informed consent process and that written informed

consent was obtained prior to participation in the study.

The Consent Forms should be revised whenever there are changes to study procedures or when new information becomes available that may affect the willingness of the patient to participate.

Patients must be re-consented to the most current version of the Consent Forms (or to a significant new information/findings addendum in accordance with applicable laws and IRB/EC policy) during their participation in the study. For any updated or revised Consent Forms, the case history or clinical records for each patient shall document the informed consent process and that written informed consent was obtained using the updated/revised Consent Forms for continued participation in the study.

A copy of each signed Consent Form must be provided to the patient or the patient's legally authorized representative. All signed and dated Consent Forms must remain in each patient's study file or in the site file and must be available for verification by study monitors at any time.

Consent Form may also include patient authorization to allow use and disclosure of personal health information in compliance with the U.S. Health Insurance Portability and Accountability Act (HIPAA) of 1996. If the site utilizes a separate Authorization Form for patient authorization for use and disclosure of personal health information under the HIPAA regulations, the review, approval, and other processes outlined above apply except that IRB review and approval may not be required per study site policies.

13.3.1 CONSENT/ASSENT AND OTHER INFORMATIONAL DOCUMENTS PROVIDED TO PARTICIPANTS

Consent forms describing in detail the study agent, study procedures, and risks are given to the participant and written documentation of informed consent is required prior to starting intervention/administering study product.

13.3.2 CONSENT PROCEDURES AND DOCUMENTATION

Informed consent process will be initiated prior to the individual's agreeing to participate in the study and continues throughout the individual's study participation. Extensive discussion of risks and possible benefits of participation will be provided to the participants and their families.

Consent forms will be IRB-approved and the participant will be asked to read and review the document. The investigator will explain the research study to the participant and answer any questions that may arise. All participants will receive a verbal explanation in terms suited to their comprehension of the purposes, procedures, and potential risks of the study and of their rights as research participants. Participants will have the opportunity to carefully review the written consent form and ask questions prior to signing. The participants will have the opportunity to discuss the

study with their surrogates or think about it prior to agreeing to participate. The participant will sign the informed consent document prior to any procedures being done specifically for the study.

The participants may withdraw consent at any time throughout the course of the trial. A copy of the informed consent document will be given to the participants for their records. The rights and welfare of the participants will be protected by emphasizing to them that the quality of their medical care will not be adversely affected if they decline to participate in this study.

The study allows the inclusion of non-English speaking and non-reading participants. Witnesses to these consent processes will be individuals not associated with the trial and will not have a conflict of interest.

